## 8. **TRANSPLANT, IMMEDIATE POST-OPERATIVE AND LONG TERM FOLLOW-UP**

### 8.1. **Transplant Details**

The following information concerning the transplant procedure will be collected:

- The organ recipient unique post-transplant patient identifier

- Total cross clamp duration in minutes (from donor cross-clamp application to removal of cross-clamp in the recipient)
- Total cold ischemia time will be collected (OCS = cold ischemic time pre and post OCS Liver perfusion)
- Any surgical complications encountered during surgery
- Use of circulatory bypass will be recorded
- Type of liver anastomosis
  - Bicaval anastomosis; or
  - Piggyback anastomosis
- The total amount of any blood product and clotting factors transfusion will be collected (pRBCs, Fresh Frozen Plasma (FFP), platelets, etc.)
- Any inotropic support needed to maintain hemodynamics will be collected
- A liver tissue biopsy will be collected from the right lobe of the transplanted liver immediately before abdominal closure in the recipient. The biopsy will be collected according to Liver Biopsy protocol in [Appendix 1](#).

## 8.2. Post-transplant Functional Assessments Day 0 – Day 30:

- **Early Liver Allograft Dysfunction (EAD) Surveillance in the first 7 days:**
  - AST level > 2000 IU/ml within the first 7 postoperative days;
  - Bilirubin  $\geq$  10 mg/dl on postoperative day 7;
  - INR  $\geq$  1.6 on postoperative day 7; or
  - Primary non-functioning graft within 7 days.
- **Inotropic Support to Maintain Hemodynamics at T0, T24 and T48 and T72 hours after ICU admission (if applicable) will be collected**
- **Initial use of Mechanical Respiratory Support:** Duration of initial post-transplant invasive ventilator support will be recorded from the time of initial admission to ICU post-Liver transplant until extubation.
- **Initial Post-Transplant ICU Stay:** Intensive care unit (ICU) admission time, and date and time when clinical order for ICU discharge is written.
- **Renal Replacement Therapy:** Need for dialysis treatments in the first 10 days post liver transplantation for patients that did not have renal replacement prior to transplantation
- **Immunosuppression Medications:** The type of immunosuppression medication and dose will be recorded at day 7 and at time of discharge from the hospital. Immunosuppression induction will be recorded if applicable.

- **Patient and Graft Survival at Day 30 and At Initial Hospital Discharge:** Patient and graft survival will be assessed on day 30 post-transplant and at initial hospital discharge post-liver transplantation.
- **Liver graft-related Serious Adverse Events:** All liver graft-related serious adverse events will be followed and documented until the investigator designates the event to be either resolved or its effect on the patient's condition stabilized.
- **Medications:** Medications used to treat all serious liver graft-related adverse event (SAE)-related will be recorded in the trial electronic database until the SAE is resolved.

These follow-ups will be attempted within  $\pm$  3 days of the designated periods except for the Early Liver Allograft Dysfunction (EAD) Surveillance, in the first 7 days which must be collected at the designated times. The evaluations may be conducted over several days.

### **8.3. Long-term Follow-up: 6 and 12 & 24 Months**

Follow-up data collection will be conducted at approximately 6, 12, and at 24 months post-transplant.

#### **8.3.1. 6 and 12-Month Follow-up**

At approximately 6- and 12-months post-transplant, the patient will be evaluated at an office visit if this is the institution's standard of care, and, if not, by phone contact by the site. The patient's medical record may be reviewed to confirm patient's answers. This follow-up will collect information on:

- Patient and graft survival
- Liver graft-related SAEs (6 months only)
- Liver graft-related re-hospitalization after initial discharge, and, if yes, the primary reason/diagnosis for the hospitalization and the length of stay
- Information will also be collected on any diagnosis of ischemic biliary complications and, if so, the method of diagnosis and treatment.

The 6 and 12-month follow-up will be collected within  $\pm$  1 month of the designated period and will be recorded on the 6- and 12-month follow-up electronic form.

#### **8.3.2. 24-Month Follow-up**

At approximately 24 months post-transplant ( $\pm$  1 month), the patient will be evaluated at an office visit if this is the institution's standard of care, and, if not, by phone contact by the site. The patient's medical record may be reviewed to confirm patient's answers. This follow-up will collect information on:

- Patient and graft survival
- Results of standard clinical practice or for cause liver biopsy will be collected (if applicable).

The 24-month follow-up will be collected within  $\pm$  1 month of the designated period and will be recorded on the 24-month follow-up electronic form.

## **9. EVALUATION OF ADVERSE EVENTS**

### **9.1. Evaluation of Liver Graft-Related Adverse Events (LGRAEs)**

Liver Graft-Related Adverse Events (LGRAEs) are those which have any untoward effect on the health or safety of the patient and that are related to the transplanted liver function (except for acute rejection). LGRAEs will be collected from the time a subject is transplanted with a liver preserved on OCS until the completion of the 30-day follow-up evaluation. A LGRAE will be followed until resolution or stabilization of the event.

### **9.2. Serious Adverse Events (SAEs)**

An adverse event will be classified as serious if it meets any of the following criteria:

- Results in, leads to, or contributes to, a death
- Is life-threatening
- Results in permanent disability or incapacity (i.e., permanent impairment of a body function or permanent damage to a body structure)
- Requires in-patient hospitalization or prolongs hospitalization
- Necessitates medical or surgical intervention to preclude a permanent disability or incapacity
- Results in fetal distress, fetal death or a congenital anomaly/birth defect.

Only liver graft-related SAEs will be followed until their resolution.

### **9.3. Anticipated and Unanticipated Adverse Events**

The investigator will assess each adverse event for whether it is anticipated or unanticipated. An unanticipated adverse event is defined as any adverse effect on health or safety, or any life-threatening problem or death caused by, or associated with, a device if that effect, problem or death was not previously identified in nature, severity or degree of incidence in the investigational plan or application (including a supplementary plan or application), or any other unanticipated serious problem associated with a device that relates to the safety, or welfare of subjects.

Adverse events are associated with liver transplant procedures and have been documented within the first 30 days after liver transplant, and are therefore anticipated. The list of events includes, but is not limited to:

• Acute rejection	• Death
• Atrial and ventricular arrhythmias	• Fever
• Bleeding	• Early liver allograft dysfunction (EAD)
• Hemodynamic instability	• Respiratory failure

- Liver primary non-function
- Bile leaks
- Hepatic artery thrombosis
- Portal vein thrombosis
- Cholangitis
- Liver abscess
- Diaphragmatic injury
- Phrenic nerve injury
- Sepsis
- Renal dysfunction and/or failure
- Hyperammonaemia
- Malignancy (post-transplant lymphoproliferative disorder (PTLD))
- Multiple organ failure
- Myocardial infarction
- Neurological dysfunction
- Hepatic dysfunction
- Diabetes due to steroid and anti-rejection medications
- Pancreatitis
- Peptic ulceration
- Gastritis
- Gastro esophageal reflux disease (GERD)
- Aspiration
- Cardiac tamponade
- Pneumo-mediastinum
- Pneumothorax
- Hemothorax
- Ascites
- Pleural effusion
- Venous thromboembolism (deep venous thrombosis [DVT])
- Pulmonary embolism (PE)
- Abdominal wound dehiscence
- Organ deemed not transplantable after retrieval
- Stroke
- Psychosis
- Ileus
- Bowel obstruction
- GI Bleeding (upper or lower)
- Cerebrovascular accident
- Peripheral vascular clotting or occlusion due insertion of mechanical support or equivalent
- Delirium, confusion and neurological complications
- Hepatic coma
- Retransplantation
- Limb gangrene due to vascular occlusion due insertion of mechanical support
- Use of mechanical circulatory support
- Coagulopathy
- Blood product transfusion
- Transfusion reaction
- Hyperacute rejection
- Anastomotic site complications; narrowing, bleeding or occlusion
- Bowel thromboembolic complications and gangrene
- Protamine and other anti-heparin medication reaction
- Heparin induced thrombocytopenia

#### **9.4. Unanticipated Adverse Device Effect (UADE)**

An UADE means any serious adverse effect on health or safety or any life-threatening problem or death caused by, or associated with, a device, if that effect, problem, or death was not previously identified or encountered before at least once in standard clinical practice, in nature, severity, or degree of incidence in the investigational plan or application (including a supplementary plan or application), or any other unanticipated serious problem associated with a device that relates to the rights, safety, or welfare of subjects.

## 9.5. Recording and Reporting of Adverse Event

All liver graft-related adverse events and serious adverse events are to be captured until post-transplant day 30 or until initial hospital discharge, whichever comes first. The description of the adverse event will include: the date of onset, duration, severity, seriousness, the relationship of the event to the trial treatment, anticipated or not, and any treatment required. All liver graft-related serious adverse events occurring during the course of the first 30 days post-transplant will be reported to TransMedics, Inc., as well as documented on the appropriate electronic case report form(s). For all liver graft-related SAEs, the investigator is required to supply any additional data that may be deemed necessary by the Sponsor. Additionally, any serious adverse events (SAE) and unanticipated adverse device effects (UADE) should be reported to TransMedics, Inc., as soon as possible after the investigator learns of the event. LGRAEs will be recorded up to the 30-day follow-up or through hospital discharge only if longer than 30 days. For any particular patient, the CEC, if required to protect patient safety, may specify a different follow-up period. The Sponsor is responsible for the classification and reporting of liver graft-related adverse events to the appropriate regulatory authorities, and for the on-going safety evaluation of the trial in accordance with ISO 14155 and governing regulatory requirements.

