## 5.4. Safety Endpoint

Safety will be analyzed principally by examination of the frequency of liver graft-related serious adverse events (LGRSAEs) up to the 30-day follow-up after transplantation. This endpoint is defined as the average number of LGRSAEs through the 30 days post-liver transplantation per subject, consisting of the following serious adverse events (at most one per type per person):

- Primary non-function (defined as irreversible graft dysfunction requiring emergency liver re-transplantation or death with the first 10 days, in the absence of immunologic or surgical causes)
- Ischemic biliary complications (ischemic biliary strictures, and non-anastomotic bile duct leaks)
- Vascular complications (liver graft-related coagulopathy, hepatic artery stenosis, hepatic artery thrombosis and portal vein thrombosis)
- Liver allograft infections (liver abscess, cholangitis, etc.).

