## APPENDIX 2. SCHEDULE OF CLINICAL ASSESSMENTS

Evaluations	
Eligibility & ID	X
Demographics/Characteristics	X
Donor Cause of Death	X
Donor Medical & Social History	X
Donor Liver Assessment	X
Donor Cross Clamp Time and Flush Detail	X
Post-Preservation Liver Biopsy and if applicable Bile duct specimen	X
OCS Preservation Parameters	X
OCS Liver Enzymes & Lactate Levels	X
Device Malfunction (if applicable)	X
Non-transplant Reasons (if applicable)	X

Evaluations	Recipient Schedule of Assessments					
	Tx. Day - Day 7 Post-Tx.	Discharge	Day 30	Month 6	Month 12	Month 24
Eligibility & Informed Consent	X					
Demographic/Characteristics	X					
Medical & Risk Factors	X					
Transplant Details	X					
Early Liver Allograft Dysfunction (EAD) Surveillance	X					
Mechanical Ventilator Support	X					
Patient Survival	X	X	X	X	X	X
Graft Survival	X	X	X	X	X	X
Immunosuppressive Meds & Induction (if applicable)	X	X				
Initial ICU & Hospital Stay	X	X				
Liver graft-related (AE's & SAE's)	X	X	X	X		
Liver graft-related re-hospitalizations				X	X	
Ischemic biliary complications				X	X	
Liver Biopsy *	X				X	X

\* ONLY tests regularly scheduled per center standard of care or performed due to a clinical cause at these timepoints will be collected.

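### The opening sentence of 9.5 stops graft-related AE and SAE capture at the earlier of Day 30 and discharge, contradicting the rest of 9.5, section 9.1, Appendix 2 and the 30-day safety endpoint

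*Combined protocol and SAP*

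**What the plan says.** Section 9.5 gives three statements on how long events are collected:

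- Its opening sentence covers graft-related AEs and SAEs, which are "captured until post-transplant day 30 or until initial hospital discharge, whichever comes first".
- A later sentence covers SAEs: "All liver graft-related serious adverse events occurring during the course of the first 30 days post-transplant will be reported" to the sponsor and entered on the electronic case report form. It makes no reference to discharge.
- A further sentence covers liver graft-related adverse events (LGRAEs): "LGRAEs will be recorded up to the 30-day follow-up or through hospital discharge only if longer than 30 days".

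Section 9.1 collects LGRAEs from transplant "until the completion of the 30-day follow-up evaluation". In the recipient schedule of Appendix 2, the row "Liver graft-related (AE's & SAE's" is marked at Discharge and separately at Day 30.

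The safety endpoint in 5.4 is the "average number of LGRSAEs through the 30 days post-liver transplantation per subject", counting at most one event of each type per person, and 10.4 repeats it. Section 10.4 also tabulates graft-related AEs. Section 10.2.2 bases the safety analysis on the mITT population, which is everyone transplanted.

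**The concern.** The opening sentence of 9.5 takes the earlier of two dates; the later LGRAE sentence takes the later of the same two. For anyone discharged before Day 30 they set different end dates for the same events, and no reading satisfies both.

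The protocol itself treats early discharge and problems after discharge as ordinary. Survival is assessed separately at discharge and at Day 30, and 8.3.1 collects "Liver graft-related re-hospitalization after initial discharge".

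Section 9.5 is where a site looks for its recording instructions, and the conflicting sentence comes first. A site that follows it can miss events between discharge and Day 30. Those events leave the numerator while the subject remains in the denominator. With up to 21 sites, different readings would also mix capture windows within one estimate, and a single-arm study has no concurrent control against which a shortfall might show.

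**Working it through.** The plan gives no figure to reproduce, and no sample size, power or error rate depends on this point. The check compares the end dates that each place sets.

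**Inputs.** Let d be the day of initial discharge and E the day on which the 30-day evaluation is done. Section 8.2 allows ±3 days for this follow-up, so E can run from 30 − 3 = Day 27 to 30 + 3 = Day 33.

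| Place | Events | Window ends |
|---|---|---|
| 9.5, opening sentence | graft-related AEs and SAEs | min(30, d) |
| 9.5, SAE sentence | graft-related SAEs | Day 30 |
| 9.5, LGRAE sentence | LGRAEs | max(30, d) |
| 9.1 | LGRAEs | E |
| Appendix 2 | graft-related AEs and SAEs | assessed at Discharge and again at Day 30 |
| 5.4 and 10.4 | graft-related SAEs | Day 30 |

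**Discharge before Day 30.** The opening sentence ends on day d, and every other row goes beyond discharge to Day 30 or, under 9.1, to the 30-day evaluation. Endpoint days left unobserved under the opening sentence are 30 − d. The documents give no length of stay, so these discharge days are assumed for illustration:

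- d = 10: 30 − 10 = 20 days
- d = 15: 30 − 15 = 15 days
- d = 20: 30 − 20 = 10 days
- d = 25: 30 − 25 = 5 days

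These are days without observation, not missed events. Converting one to the other would need event timing, which the documents do not give.

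**Discharge after Day 30.** The 30-day endpoint loses nothing. The two 9.5 rules still differ by d − 30 days: the LGRAE sentence runs to discharge, the opening sentence stops at Day 30. This matters for the graft-related AE tabulations in 10.4, which state no 30-day limit. Section 9.1 has no extension to a late discharge either.

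**Early evaluation under 9.1.** If E = 27, section 9.1 read literally closes collection 30 − 27 = 3 days before the endpoint window does. So 9.1 also needs adjustment before it guarantees the full window.

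**Direction.** Missed events can only lower the average per subject and the counts and subject percentages in the graft-related AE tabulations, because the mITT denominator is fixed by transplantation.

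**What is not touched.** The synopsis describes the safety analysis as descriptive, so no test depends on it. The stopping rule in 10.7 uses death by Day 30, which is collected separately.

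**The case against.** The strongest reply is that the principal endpoint counts only SAEs, and these have several other routes into the data:

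- The SAE sentence of 9.5 covers the first 30 days without a discharge limit.
- Another sentence of 9.5 asks for any SAE to be reported as soon as possible once the investigator learns of it, with no end date.
- Section 8.2, headed for Day 0 to Day 30, has all graft-related SAEs followed and documented until resolved or stable.
- Primary non-function needs re-transplantation or death within 10 days, and patient and graft survival are collected at Day 30.
- Ischemic biliary complications are collected at 6 and 12 months, and 8.3.1 lists "Liver graft-related SAEs (6 months only").

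Most of this stands. It leaves vascular complications and graft infections as the main residual exposure within the endpoint, and only where a site follows the opening sentence over everything else. It does not close the gap. Prompt reporting depends on the investigator hearing of the event, and nothing says that the 6-month collection reaches back to discharge or feeds the 30-day count. Nor does it cover non-serious graft-related AEs, because 8.3.1 collects only SAEs at Month 6.

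A reader might also infer a contradiction at Month 6, since the Appendix 2 row label names both AEs and SAEs while the synopsis and 8.3.1 say SAEs only. The documents do not support giving that weight: 4.2 presents Appendix 2 as a summary of follow-up, the row carries one combined label for all visits, and 9.5 need not repeat a separate follow-up item.

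**Conclusion.** The contradiction is certain and can be seen within 9.5 alone; it does not depend on how the Appendix 2 columns are read. It is an inconsistency in data-capture wording, and no analysis method is at fault.

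The effect is conditional. At a site that follows the opening sentence, graft-related events after discharge and before Day 30 can be missed, and the safety summaries can then only be biased downward. The amount cannot be estimated, because length of stay, event timing and site practice are all undocumented. Non-serious graft-related AEs are the most exposed; SAEs are substantially but not fully protected.

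Two stronger readings should be resisted. A reader might infer that the 30-day safety endpoint is materially understated; the documents show a possible direction, not a size, and no evidence that sites follow the opening sentence. A reader might equally infer that nothing is lost wherever the other passages are followed; that fails too, because 9.1 can close as early as Day 27 and has no extension for stays beyond Day 30.

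**What to change.** - In 9.5, replace the opening rule so that graft-related AEs and SAEs are captured through Day 30 for every subject regardless of discharge, and through discharge when the initial stay exceeds 30 days. This adopts the protocol's own later sentence.
- Align 9.1 with the same window, adding that capture runs through Day 30 even when the 30-day evaluation falls early in its ±3-day allowance.
- Notify sites of the corrected rule.

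The cost is a short protocol correction and a site memo. Appendix 2 already schedules a Day 30 assessment of these events, so the only added work is a brief record check or contact for subjects evaluated on Days 27 to 29. The reported event rate may come out somewhat higher. Aligning the Month 6 row label in Appendix 2 with 8.3.1 would be optional tidying.

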### 10.4. Analysis of Safety

Safety will be analyzed principally by examination of the frequency of liver graft-related serious adverse events (SAEs) up to the 30-day follow-up after transplantation. This endpoint is defined as the average number of liver graft-related serious adverse events through the 30 days post-liver transplantation per subject, consisting of the following serious adverse events (at most one per type per person):

- Primary non-function (defined as irreversible graft dysfunction requiring emergency liver re-transplantation or death within the first 10 days, in the absence of immunologic or surgical causes)
- Ischemic biliary complications (ischemic biliary strictures, and non-anastomotic bile duct leaks)
- Vascular complications (liver graft-related coagulopathy, hepatic artery stenosis, hepatic artery thrombosis and portal vein thrombosis)
- Liver allograft infections (liver abscess, cholangitis, etc.).

In addition, the numbers and percentages of subjects experiencing at least one liver graft-related AE, at least one (definitely or probably-related) device-related AE, at least one unanticipated AE, and at least one serious AE, and the number and percentage of deaths will all

be tabulated. Also, the number of liver graft-related adverse events and the number and percentage of subjects experiencing liver graft-related adverse events will be tabulated by system organ class and preferred term using MedDRA. A similar analysis will be performed for LGRSAEs. AEs will also be tabulated at the event level by system organ class and preferred term and the relationship of the adverse event to the device using counts and percentages. Similar analyses will be performed by the severity of the adverse event.

For livers that are not transplanted, the reason(s) for non-transplantation (including device failure) will be summarized using counts and percentages. The number and percentage of donor livers in the Donor Liver Population for which these was a device failure will also be presented.

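### The additional safety tables in section 10.4 have no onset cut-off, while sections 9.1, 9.5 and 8.3.1 and Appendix 2 give incompatible collection windows for graft-related AEs and SAEs

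*Combined protocol and SAP*

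**What the plan says.** **Collection.** Section 9.1 collects liver graft-related AEs (LGRAEs) from transplant "until the completion of the 30-day follow-up evaluation". Section 9.5 contains two rules. Its opening sentence has graft-related AEs and SAEs "captured until post-transplant day 30 or until initial hospital discharge, whichever comes first". Further down it says "LGRAEs will be recorded up to the 30-day follow-up or through hospital discharge only if longer than 30 days", and adds: "For any particular patient, the CEC, if required to protect patient safety, may specify a different follow-up period". Section 8.3.1, like the synopsis, lists "Liver graft-related SAEs (6 months only") among the items collected from every recipient at the long-term visits. Appendix 2 has a row "Liver graft-related (AE's & SAE's") marked at transplant to Day 7, discharge, Day 30 and Month 6.

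**Analysis.** Section 10.4 defines the principal endpoint as an average count of graft-related SAEs through 30 days. It then continues: "In addition, the numbers and percentages of subjects experiencing at least one liver graft-related AE", followed by device-related, unanticipated and serious AEs, deaths, MedDRA tables for LGRAEs and graft-related SAEs, and event-level tables by device relationship and severity. None of these carries a time limit. Section 10.2.2 bases the safety analysis on the mITT population, that is, all transplanted subjects.

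**The concern.** A percentage of subjects with at least one event is a risk only if everyone in the denominator was watched for the same stated period. Here the period depends on which rule a site follows. Under the later sentence of 9.5 it also depends on length of stay, which is itself tied to how the graft is doing. With no cut-off in 10.4, whatever has been collected goes into the table.

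The resulting figures would be neither 30-day risks nor risks over any other fixed period. They could not be set beside the 30-day principal endpoint or a fixed-window rate from elsewhere, although a reader of the report would naturally do so. Deaths show the gap most plainly: survival is followed to Month 24, and the death count in 10.4 has no window.

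**Working it through.** **1. The windows side by side**

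| Source | Events | Collection ends |
|---|---|---|
| 9.1 | LGRAEs | 30-day evaluation |
| 9.5, opening sentence | Graft-related AEs and SAEs | Day 30 or discharge, whichever is earlier |
| 9.5, later sentence | LGRAEs | 30-day follow-up, or discharge if the stay exceeds 30 days |
| 9.5, CEC sentence | Individual patients | Another period, if patient safety requires it |
| 8.3.1 and synopsis | Graft-related SAEs, all recipients | Month 6 |
| Appendix 2 | Graft-related AEs and SAEs, all recipients | Month 6 |
| 10.4, principal endpoint | Listed graft-related SAEs | 30 days |
| 10.4, further tables | AEs, SAEs, deaths | Not stated |

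Even 9.1 is not quite a common window. Section 8.2 allows the Day 30 assessment to fall three days either side, so collection could end anywhere from Day 27 to Day 33.

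**2. What can be computed**

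The plan states no AE rate, length of stay or share of long-stay recipients. The 184 subjects come from the enrolment rate in the earlier trial (10.5). There is no plan figure to reproduce, and every input below except 184 is an assumption.

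**3. Prolonged-stay extension (later sentence of 9.5)**

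Let f be the share still in hospital after Day 30, p their 30-day LGRAE risk, and q the chance of a first LGRAE after Day 30 while in hospital, given none before.

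Added percentage = f × (1 − p) × q

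- Low: 0.05 × 0.40 × 0.10 = 0.20 points, or 0.4 of 184 subjects.
- Middle (f = 0.10, q = 0.30): 1.2 points (p = 0.60) to 2.1 points (p = 0.30), about 2 to 4 subjects.
- High: 0.20 × 0.70 × 0.50 = 7.0 points, or 12.9 subjects.

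A hazard model serves as a cross-check. Take a 30% 30-day risk in short-stay recipients, so h = −ln(0.70)/30 = 0.0119 per day. Long-stay recipients have hazard k·h, and their extra stay is exponential with mean 1/λ.

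Long-stay risk = 1 − exp(−30kh) × λ/(λ + kh)

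- f = 5%, k = 1, mean 15 days: 1 − 0.70 × 0.849 = 0.406. Excess 0.05 × (0.406 − 0.30) = 0.5 points.
- f = 20%, k = 2, mean 30 days: 1 − 0.49 × 0.584 = 0.714. Excess 0.20 × (0.714 − 0.51) = 4.1 points.

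A constant hazard is the extreme case, since early complications usually become less frequent with time. With cumulative hazard k × 0.357 × (t/30)^s, where 0.357 = −ln(0.70), and s = 0.3 to 0.5, the same inputs give 0.14 points (f = 5%, k = 1, mean 15 days, s = 0.3) to 2.1 points (f = 20%, k = 2, mean 30 days, s = 0.5: 0.20 × (0.617 − 0.51)).

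**4. Earlier-of rule (opening sentence of 9.5)**

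With constant hazard and discharge on day d, captured risk = 1 − (1 − R)^(d/30), where R is the true 30-day risk.

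- R = 20%: 7.2% captured at d = 10, 9.9% at d = 14.
- R = 40%: 15.7% and 21.2%.

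The error now runs downward, so even its direction depends on which sentence a site follows.

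**5. Month 6**

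If Month 6 SAEs entered the graft-related SAE table, an assumed 10% 30-day risk would become 1 − 0.9^(6^s): 16.5%, 22.7% and 46.9% for s = 0.3, 0.5 and 1. No section says they will be pooled, and none says they will not.

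**The case against.** The strongest reply is that the harm is small. The principal safety endpoint already has a 30-day limit, the trial has one arm, safety is descriptive and no test is planned. Sections 10.3 and 10.6 defer detail to an SAP to be finalised before lock, and 9.5 records the onset date, so a cut-off can still be applied later. Most of this stands and limits the weight of the point. It does not supply a cut-off, and an onset date cannot recover events that were never collected after an early discharge.

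Three stronger readings are tempting, and the documents support none of them.

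- A reader might infer that collection after Day 30 is confined to recipients still in hospital or picked out by the CEC. Section 8.3.1 and Appendix 2 collect graft-related SAEs at Month 6 from every recipient, Appendix 2 adds AEs, 9.1 has no hospital extension, and the CEC exception is conditional on patient safety. The length-of-stay dependence applies mainly to non-serious LGRAEs under one sentence of 9.5.
- A reader might infer that the principal endpoint is inflated. The over-long window cannot reach it; only the earlier-of rule could affect it, by under-capture.
- A reader might infer that long-stay recipients will be reported as more event-prone. Section 10.4 plans no table by length of stay.

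It can also be said that harmonising collection to 9.1 would remove most of the problem. It would for LGRAEs, but the CEC exception, Month 6 collection and the unlimited death count would remain, so 10.4 needs a stated window in any case.

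**Conclusion.** The point holds for the further tables in 10.4: they name no onset window, and the collection rules behind them conflict. Followed as written, the mITT percentages can combine LGRAEs beyond Day 30, mainly from long-stay recipients, with SAEs possibly to Month 6 for everyone, and could miss events after early discharge.

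The size cannot be derived from the documents. Across the assumed inputs (5–20% in hospital beyond Day 30, with the risks and hazards shown above), the prolonged-stay extension adds roughly 0.1 to 7 points to the percentage with at least one LGRAE. The upper part of that range needs a large long-stay share and a high late event rate. The problem is one of interpretation of descriptive tables. It should be fixed because the remedy is cheap, but it does not undermine the principal safety endpoint.

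**What to change.** - **10.4 and SAP:** state that every count, percentage and MedDRA table of AEs, SAEs and deaths covers events with onset (or death) from transplant through calendar Day 30, for all mITT subjects. Put later events (prolonged stay, CEC extension, Month 6) in a separate labelled table or listing.
- **9.1 and both sentences of 9.5:** reconcile them to one collection rule under which every recipient is observed through Day 30 regardless of discharge date, including recipients whose Day 30 assessment falls early. Without this, a Day 30 cut would label the tables as 30-day while early discharges were still under-observed. The CEC exception can stay; only the placement of its events in the tables changes.
- **8.3.1 and Appendix 2:** make the Month 6 entries agree, either SAEs only or AEs and SAEs.

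The cost is a sentence in 10.4, one extra table or listing, and text corrections in the collection sections. No extra patients are needed. Onset date is already recorded and Appendix 2 already schedules AE collection at Day 30, so added data work is limited to sites that would have stopped at discharge or at an early visit. Headline AE percentages will be slightly lower than without a cut-off.
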